10.7 POSTOPERATIVE PROCEDURES

Postoperatively, subjects will be examined according to the schedule in Section 10.2, Visit Schedule. One or both implanted eyes will be examined at 1-week and 3-month visits.

The postoperative case report form will include the following information, although not all are required at every visit:

UNCORRECTED DISTANCE VISUAL ACUITY

Monocular UCDVA is to be measured using a standard Snellen convention.

MANIFEST REFRACTION AND BEST CORRECTED DISTANCE VISUAL ACUITY

Manifest refraction is to be performed per the site's usual technique. Monocular BCDVA is to be measured using a standard Snellen convention.

MEDICAL FINDINGS

At each postoperative visit presence or absence of any medical or lens findings, complications, or serious or device-related adverse events will be noted.

ND:YAG CAPSULOTOMY

If an Nd:YAG capsulotomy is necessary, it is recommended that the procedure be performed at least 1 week prior to a study visit.

KERATOMETRY AND REFRACTION

Corneal curvature and refraction are to be measured using the investigator's usual methods. It is recommended that the same methods be used for all study subjects at the site for the duration of the study.

SURGEON SATISFACTION QUESTIONNAIRE (SSQ)

This 3-item questionnaire is self-administered and should be completed by the surgeon. The purpose of this questionnaire is to collect surgeon satisfaction with the clinical outcomes (e.g., rotational stability, uncorrected distance visual acuity) of the eye(s) implanted with the study lens.

Surgeon satisfaction with rotational stability will be collected for each implanted eye using a single-item from the SSQ at the 1-week visit. At the 3-month visit, surgeon feedback from the 3-item SSQ will be collected for each implanted eye.

SURGEON EXPERIENCE QUESTIONNAIRE (SEQ)

The surgeon experience questionnaire is a 5-item questionnaire that evaluates the surgeons' overall experience with the study lens in comparison to their historical experience with their preferred toric IOL (monofocal and presbyopia-correcting). This questionnaire is self-administered and should be completed only once after the last follow-up study visit (last subject's 3-month visit) for the study.

MEDICATIONS

Postoperative ocular medications should be used as is customary for each investigator and recorded in the source document for each subject, as appropriate. Only medications required for treatment of an SAE will be recorded on the case report forms.

ADVERSE EVENTS

Subjects should be assessed at each visit for the occurrence of and/or change in status of any adverse events, particularly serious and/or device-related adverse events. See Section 11, Adverse Events, and Error! Reference source not found. for further information.

10.8 EXIT OF SUBJECTS

An Exit Case Report Form will be completed for all subjects, either when they complete the study or if they exit early.

It is the responsibility of the investigator to provide complete follow-up data to JJSV for each subject, and every attempt should be made to gather that complete follow-up data for all subjects enrolled as missing data can have a negative effect on the study results. Patients who would be traveling, relocating or otherwise unavailable for postoperative follow-up visits should not be chosen for this clinical study.

Subjects will be discontinued from the study if the study lens is removed and the fellow eye does not have a study IOL or if the subject dies. Subjects will be considered "lost-to-follow-up" from the study only if irretrievably lost for unavoidable reasons such as: subject moved/unable to locate, subject uncooperative/refuses further study participation, subject ill/unable to travel.

A subject will be considered a screen failure if he/she does not meet the enrollment criteria. A subject will also be considered a screen failure if he/she does not undergo surgery or receive a study lens for various reasons including: the planned implant being aborted due to surgical complications, the subject withdrawing consent prior to treatment or the subject died prior to

treatment. If a subject receives at least one study lens, he/she is to be followed according to the protocol.

If a subject is exited early from the study, the investigator will submit an Exit Case Report Form to JJSV indicating the reason for study exit. In the event of a lens removal or other serious adverse event, the subject may be exited from the study; however, efforts must be made by the investigator to follow the subject until resolution of the adverse event.

All study subjects are to be instructed to undergo regular eye examinations at least yearly and to return to their doctor if any eye complications are experienced in the interim.

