11.5 ADVERSE EVENT FOLLOW-UP

For every adverse event, appropriate measures should be undertaken to treat and/or monitor the subject until resolution occurs. Obtain and maintain in the subject's files all pertinent medical data relating to the event including the subject's medical records and medical reports and/or judgments from colleagues or outside specialists who assisted in the treatment and follow-up of the subject. The investigator should keep JJSV closely informed as to the outcome of serious and/or device-related adverse events, thereby allowing JJSV to comply with the appropriate regulatory reporting requirements. An Unscheduled Visit form should be completed each time the subject returns to the investigator or other specialist(s) for follow-up of a serious and/or device-related adverse event until resolution of the event and the SAE/ADE form should be updated as necessary (e.g., to document the resolution of the SAE/ADE). Any subject who is exited from the study due to a serious and/or device-related adverse event will be followed until the outcome is determined.

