19. TERMINATION OF THE INVESTIGATION

JJSV can suspend or terminate the clinical investigation at any time for reasons it determines appropriate. Additionally, the investigator, or JJSV, may stop a subject's participation at any time. However, no suspension of the study would be made to disadvantage the study subjects. Following suspension of the study for any reason, all study subjects who have already received treatment would continue to be followed through completion of the study visit schedule.

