20.1 ANALYSIS POPULATION

For the primary endpoint, the primary analysis population will be all eyes implanted with a toric IOL (model ZCU150 through ZCU600) and with available data at the 3-month visit. For other endpoints, all eyes implanted with a toric IOL model ZCU150 to ZCU600 and with available data at the key timepoint for that endpoint will be used. In addition, data for the primary endpoint will also be evaluated by IOL model for lower-cylinder IOLs (ZCU150), medium-cylinder IOLs (ZCU225 to ZCU375) and for extended higher-cylinder IOLs (ZCU450, ZCU525 and ZCU600). For the surgeon preference questionnaire (SPQ) and the surgeon experience questionnaire (SEQ), the analysis population will be surgeons responding to these questionnaires.

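### Section 10.8 permits study exit after any serious adverse event with the lens still in place, and nothing then secures the 3-month rating, so poor-outcome eyes can drop out of the primary proportion

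*Combined protocol and SAP*

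**What the plan says.** Section 10.8 contains four statements that bear on the point.

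- Duty to follow treated subjects: "If a subject receives at least one study lens, he/she is to be followed according to the protocol".
- Duty of completeness: "every attempt should be made to gather that complete follow-up data for all subjects enrolled".
- Mandatory discontinuation, apart from death: "Subjects will be discontinued from the study if the study lens is removed and the fellow eye does not have a study IOL".
- Permission to exit: "In the event of a lens removal or other serious adverse event, the subject may be exited from the study". The sentence goes on to say that "efforts must be made by the investigator to follow the subject until resolution of the adverse event".

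Section 11.5 adds: "Any subject who is exited from the study due to a serious and/or device-related adverse event will be followed until the outcome is determined". Section 19 says that the investigator or the sponsor "may stop a subject's participation at any time", although treated subjects complete the visit schedule if the whole study is suspended.

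On the analysis side, the primary endpoint (6.1, 20.2) is the surgeon's overall satisfaction rating at 3 months, item 1 of the SSQ. Attachment C has it completed after the 3-month visit. Section 20.1 restricts the primary population to implanted eyes "with available data at the 3-month visit". Section 20 has no rule for implanted eyes that lack this rating and no sensitivity analysis.

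**The concern.** The permission to exit covers every SAE, whether or not the lens stays in. The study-specific SAE list in 11.1 includes outcomes in eyes that can keep the lens: rotation, tilt or decentration treated by repositioning, surgery for residual refractive error, and macular edema with best corrected acuity of 20/40 or worse. Rotation and residual error are the outcomes that a toric lens study most needs to capture.

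The study is open-label and single-arm, and the surgeon completes the SSQ. The treating surgeon, who will often be the investigator, can therefore influence whether an eye with a poor result reaches the visit at which he or she would rate it. Loss from the primary analysis can then depend on the outcome. With up to 50 sites, the duty to follow and the permission to exit may also be applied differently from site to site.

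**Working it through.** **Step 1: trace an eye after an SAE with the lens in place.**

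- Exit is permitted (10.8), and participation can also be stopped under 19.
- Required afterwards: follow-up of the event until it resolves or its outcome is known (10.8, 11.5).
- Not required afterwards: the 3-month visit or the SSQ. The Unscheduled Visit form (10.9) may record acuity and refraction, but the SSQ is not among its items. The 1-week visit collects only the SSQ item on rotational stability, not the overall rating.
- Analysis: without a 3-month rating the eye is outside the 20.1 population.

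**Step 2: reproduce the plan's precision (20.4).** Inputs are n = 1000 eyes and p = 0.95. The Wald half-width is 1.96 × √(0.95 × 0.05 / 1000) = 0.0135, or 1.35 points. With a continuity correction of 1/(2 × 1000) it is 1.40 points. Both agree with the stated 1.4%, so the sample-size figure is not in error. The issue is bias, which this interval does not cover.

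**Step 3: illustrate the size.** The following are assumptions, not figures from the documents: SAE rate s (lens in place) of 1% or 3%; 50% of SAE eyes and 96% of other eyes rated 4 or 5; share e of SAE eyes exited of one half or all.

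True proportion = (1 − s) × 0.96 + s × 0.50

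Reported proportion = [(1 − s) × 0.96 + s(1 − e) × 0.50] / (1 − s·e)

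Per 1000 implanted eyes:

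| SAE rate | True | Half exited | All exited |
|---|---|---|---|
| 1% | (950.4 + 5)/1000 = 95.5% | (950.4 + 2.5)/995 = 95.8% (+0.2) | 950.4/990 = 96.0% (+0.5) |
| 3% | (931.2 + 15)/1000 = 94.6% | (931.2 + 7.5)/985 = 95.3% (+0.7) | 931.2/970 = 96.0% (+1.4) |

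**Step 4: vary the starting point.** Take the plan's 95%, that is 950 satisfied of 1000 implanted eyes, and let k eyes exit.

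- All exited eyes unsatisfied: k = 10 gives 950/990 = 95.96% (+0.96 points); k = 15 gives 950/985 = 96.45% (+1.45 points, above the 1.35-point half-width).
- Half of them unsatisfied: k = 10 gives 945/990 = 95.45% (+0.45 points).
- Exited eyes like the rest (5% unsatisfied): no shift.

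**Step 5: what a conservative sensitivity analysis would show.** If 950 of 1000 available eyes are satisfied and k further eyes exited after an SAE are counted as not satisfied, the result is 950/1010 = 94.1% for k = 10 and 950/1030 = 92.2% for k = 30.

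**The case against.** Several stronger readings are tempting, and the documents do not support them.

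- *The two sentences in 10.8 contradict each other outright.* The follow-up sentence closes the paragraph on screen failures, and the protocol to be followed includes the exit rule. The conflict is one of intent, not of logic. Still, on that reading the follow-up sentence adds little, and it sits badly with the completeness duty and with section 19, which keeps treated subjects in follow-up after a suspension.
- *The worst eyes are removed.* The wording is permissive, and 10.8 and 15.1 both press for complete data. SAEs also include non-ocular events such as hospitalization. Under Note 2 in 11.1, raised pressure is serious only if present at the last visit, and uveitis only if it persists beyond 3 months, so these can rarely cause exit before the 60-120 day window.
- *All 3-month-type data are lost.* Uncorrected acuity is also measured at 1 week, and 11.5 calls for an Unscheduled Visit form at each return for the event, on which acuity and refraction may be recorded. Only the overall SSQ rating clearly has no route.
- *The healthy fellow eye leaves too.* This is possible, because exit is worded by subject. It is not mandated: eyes are tracked individually (10.1), and mandatory discontinuation after lens removal depends on the fellow eye having no study lens.
- *The bias is 1.4 points.* That needs an assumed 3% SAE rate with every such eye exited.

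It is also fair to say that the study is descriptive with no success threshold, so no formal decision turns on the shift. Exit reasons go on the Exit Case Report Form, and accountability and adverse events are reported (20.3), so these eyes are visible in the report. They are still absent from the headline proportion, and no planned analysis shows what their absence does to it.

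**Conclusion.** The concern stands as a permitted gap. The plan allows exit after an SAE with a study lens in place, requires only event follow-up afterwards, has no route to the primary rating, and analyses available data without a missing-data rule. Loss that depends on outcome is therefore possible, partly at the rater's discretion, and the likely direction is upward.

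The size cannot be known from the documents. Under the step 3 assumptions it ranges from +0.2 to +1.4 points, the top of the range equalling the stated half-width. It is zero if exited eyes resemble the rest. This merits a change because the remedy is cheap, but nothing in the documents shows that the reported result will be materially wrong.

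**What to change.** 1. Reconcile the exit and follow-up statements in 10.8, 11.5 and 19, so that an SAE with a study lens in place does not by itself end study data collection. Editing 10.8 alone would leave the general power in 19 untouched.
2. Record exit by eye on the Exit Case Report Form, and keep a fellow study eye in follow-up.
3. Where an implanted eye still will not reach the 3-month visit, have the surgeon complete the SSQ at exit, with its date and the exit reason.
4. Keep the 3-month available-data proportion as the primary result. Pooling exit ratings into it would change the endpoint, because an early rating may precede the outcome of a repositioning, and for deaths or losses the surgeon may have only 1-week data.
5. Report beside it (a) the proportion over all implanted eyes using exit ratings, and (b) one counting eyes exited after an SAE as not satisfied. Tabulate exits by reason.

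The cost is a wording change in three sections, an eye field on an existing form, and a 3-item questionnaire for what should be few eyes, completed by surgeons already in the study. No visits are added beyond those planned. The satisfaction figures reported beside the primary result may be slightly less favourable.

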10.9 UNSCHEDULED VISITS

During the study period, if a non-protocol-required visit is done for the purpose of medically-indicated follow-up for either study eye, data from this visit should be submitted using the Unscheduled Visit CRF. The need for unscheduled visits is at the investigator's discretion. Specific examinations to be performed at unscheduled visits are also at the discretion of the investigator (based on the reason for the unscheduled visit), and data are to be recorded in the appropriate section of the case report form.

Data to be collected may include:

- Monocular UCDVA
- Manifest Refraction and monocular BCDVA
- Intraocular pressure
- Medical and/or lens findings, complications
- Serious and/or Device-Related Adverse events
- Ocular Medications

10.10 PROTOCOL DEVIATIONS

Any departure from the protocol procedures represents a protocol deviation. Protocol deviations may be subject-based (e.g., enrollment criteria, informed consent deviation, etc.) or procedural-based (e.g., out-of-interval visits, non-compliance with testing procedures, etc.).

Any deviation made to protect the life or physical well-being of a subject in an emergency, as well as any use of the study device without obtaining informed consent, must be reported to JJSV within 5 working days.

Protocol deviations will be monitored and managed by JJSV, and if the non-compliance is persistent or egregious, JJSV may act, including but not limited to termination of the investigator's participation in the study. The investigator is also responsible for informing the reviewing IRB of instances of protocol non-compliance in accordance with the IRB

11. ADVERSE EVENTS AND PRODUCT COMPLAINTS

11.1 ADVERSE EVENT DEFINITIONS

Adverse Event (AE)

An adverse event is defined (following ISO 14155) as any untoward medical occurrence, unintended disease or injury, or untoward clinical signs (including abnormal laboratory findings) in subjects, users or other persons, whether or not related to the study device.

Serious Adverse Event (SAE)

An adverse event is considered serious (following ISO 14155) if it is an untoward occurrence which may or may not be related to use of the study device that

- Is sight- or life-threatening,
- Results in death,
- Requires inpatient hospitalization or prolongation of hospitalization (a planned hospitalization for a pre-existing condition without a serious deterioration in health is not considered a serious adverse event),
- Results in permanent impairment of a body structure or body function,
- Necessitates medical or surgical intervention to prevent permanent impairment to a body structure or function, or,
- Results in fetal distress, fetal death or a congenital abnormality or birth defect

Device-Related Adverse Event/Adverse Device Effect (ADE)

A device-related adverse event is defined as any adverse event that is believed to be definitely, probably or possibly related to the study device (following the guidelines in Section 11.4, Causal Relationship). A device-related event is also considered an adverse device effect (ADE; following ISO 14155) resulting from the use of the study device that may result from user error, insufficiencies or inadequacies in the instructions for use, deployment, implantation, installation, operation or any malfunction of the device.

Study-Specific Serious Anticipated Adverse Events

The following is a list including, but not limited to, ocular serious adverse events that are anticipated and must be reported to JJSV for this study. Any events that are unlikely but anticipated (i.e., endophthalmitis or toxic anterior segment syndrome) will be reported to FDA and other appropriate regulatory agencies.

- Endophthalmitis/Intraocular infection
- Hypopyon
- Hyphema
- IOL dislocation

- Cystoid macular edema: Macular edema diagnosed by clinical examination and adjunct testing (e.g. OCT, FA) resulting in BCDVA of 20/40 or worse at 1 month or later
- Pupillary block
- Retinal detachment/tear
- Corneal edema
- Chronic iritis or uveitis
- Raised IOP that persists (i.e., is present at the last study visit)
- Toxic anterior segment syndrome (TASS)
- Visual symptoms requiring secondary surgical intervention (e.g., lens removal)
- Tilt, decentration, IOL rotation requiring secondary surgical intervention (e.g., repositioning)
- Residual refractive error resulting in a secondary surgical intervention
- Retained lens material resulting in secondary surgical intervention

NOTE 1: *Wound burps during the first week postoperatively, suture removal, planned blepharoplasty and Nd:YAG capsulotomy (for PCO) are not considered adverse events for this study.*

NOTE 2: *Corneal edema, and chronic anterior uveitis/iritis will be considered serious if corneal edema resulting in BCDVA of 20/40 or worse at 1 month or later; and Grade 1+ uveitis/iritis persists for greater than 3 months after surgery). Raised IOP requiring treatment (Elevation of IOP \geq 10 mmHg above baseline to a minimum of 25 mmHg) will be considered serious if present at the last study visit.*

Unanticipated Adverse Device Effect (UADE)/Unanticipated Serious Adverse Device Effect (USADE)

Any USADE (ISO 14155) is defined as any serious adverse effect on health or safety or any life-threatening problem or death caused by, or associated with, a device, if that effect, problem, or death was not previously identified in nature, severity, or degree of incidence in the investigational plan (i.e., this protocol), application (including a supplementary plan or application), or risk assessment, or any other unanticipated serious problem associated with a device that relates to the rights, safety, or welfare of subjects.

11.2 PRODUCT COMPLAINT/DEVICE DEFICIENCY DEFINITION

A product complaint/device deficiency is defined (21 CFR 820.3(b) and ISO 14155) as any alleged deficiency related to the identity, quality, durability, reliability, safety, effectiveness, or performance of a device. This may include malfunctions, user error and inadequacies in labeling. Product complaints can pertain to any marketed JJSV device being used in the study as well as the investigational device. The investigator is to assess whether the deficiency could have led to a serious adverse event without suitable action or intervention or under less fortunate circumstances.

11.3 ADVERSE EVENT AND COMPLAINT REPORTING REQUIREMENTS

All adverse events and any complaint encountered using any JJSV product, regardless of severity and whether or not attributed to the study device(s), are to be reported to JJSV and recorded on the case report form corresponding to the visit during which awareness of the event occurred. Adverse events are also to be reported to the reviewing IRB as per their reporting requirements. If required, adverse events will be reported to the appropriate regulatory agencies (e.g., FDA) according to all applicable laws and regulations. Specific instructions on notification procedures to JJSV are included in Error! Reference source not found..

General guidelines are provided below:

Adverse Event Reporting

An adverse event that is not serious or device-related is to be reported to JJSV in a timely manner. Notification of non-serious and non-device-related adverse events will occur by submitting events on the CRF when noted. Such adverse events are also to be reported to the reviewing IRB per their reporting requirements.

Complaints/Device Deficiency Reporting

A general product complaint or device deficiency is to be reported to JJSV in a timely manner. Notification of complaints/device deficiencies will occur by either submitting complaints on the CRF when the complaint occurred (e.g., operative form) or by a phone call to the Sponsor. Any device deficiency that could have led to a serious adverse event without suitable action or intervention, or under less fortunate circumstances, must be reported to the sponsor immediately (no later than 24 hours after detection). Device deficiencies that could have led to a serious adverse event should also be reported to the investigator's IRB per their reporting requirements.

Serious and/or Device-Related Adverse Event Reporting

Serious and/or device-related events (ADEs) are to be documented using the SAE/ADE Detailed Page. In the event of a serious adverse event (SAE), which may or may not be related to use of the study device, JJSV must be notified immediately (no later than 48 hours after detection). Any SAE is to be reported by phone (and/or email) and by submitting a completed SAE/ADE Detailed Page. Any SAE or device-related AE should also be reported to the investigator's IRB per their reporting requirements.

Unanticipated Adverse Device Effect (UADE)/Unanticipated Serious Adverse Device Effect (USADE) Reporting

If during the study, a serious adverse event occurs that may reasonably be regarded as device-related and was not previously expected in nature, severity, or degree of incidence, the investigator is to report the UADE/USADE to JJSV within 48 hours, and to the investigator's IRB as soon as possible (and no later than 10 working days after learning of the event).

